## 6.2 SERIOUS ADVERSE EVENTS

All Serious Adverse Events (SAEs) will be reported to the sponsor within 24 hours of awareness of the event. An AE will be considered serious if it meets any of the following criteria:

- Events resulting in death.
- Life-threatening events
- Events requiring hospitalization or prolongation of existing hospitalization.
- Events resulting in persistent or significant disability/incapacity.

- Events not meeting any of the above criteria deemed to be serious by the Investigator.

### 6.3 DEVICE INCIDENTS REPORTING

Study drug administered via the ELLIPTA device is a drug/device combination product. All device incidents should be notified to the sponsor. A Medical Device Incident is any malfunction or deterioration in the characteristics and/or performance of a device, as well as any inadequacy in the labelling or the instructions for use which, directly or indirectly, might lead to or might have led to the death of a patient, or USER or of other persons or to a serious deterioration in their state of health and a Serious Adverse Device Effect (SADE) that has resulted in any of the consequences characteristic of a serious adverse event and any device deficiency that might have led to an SAE if appropriate action had not been taken, intervention had not occurred, or circumstance had been less fortunate. Not all incidents lead to death or serious deterioration in health. The non-occurrence of such a result might have been due to other fortunate circumstances or to the intervention of health care personnel. It is sufficient that: an incident associated with a device happened; and the incident was such that, if it occurred again, it might lead to death or serious deterioration in health.

Device incidents should be reported as outlined below, and not as a safety event.

It is possible for a reportable safety event to occur at the same time as a device incident. Safety events are reported as described in Section 5.1 and should be reported in parallel as an AE/SAE as appropriate.

If a device incident is detected, the following process should be followed:

- Report the incident to the sponsor using the Combination Product with Device Deficiency/Incident Report Form within 24 hours of awareness of the incident

- Arrange for a new device to be provided if not already done so by a pharmacy/prescription.

## 6.4 COVID-19 CONSIDERATIONS

It is standard practice for patients admitted with respiratory symptoms to receive SARS-CoV-2 testing at the time of admission. The study will not require additional testing but will record results of any additional SARS-CoV-2 testing that occurs during hospitalization.

Patients with positive SARS-CoV-2 test at the time of admission or in the time between admission and enrollment will be excluded from the study. Patients with positive SARS-CoV-2 test after the time of enrollment will be withdrawn from the study and will continue to receive care according to institutional standard practice.

## 6.5 PREGNANCY REPORTING

If pregnancy occurs in a female participant, the pregnancy should be reported as outlined below.

- Details of all pregnancies in female participants will be collected after the start of study intervention and until the safety follow-up visit.
- If a pregnancy is reported, the investigator will record pregnancy information on the appropriate form and submit it to the sponsor within 24 hours of learning of the pregnancy. While pregnancy itself is not considered to be an AE or SAE, any pregnancy complication or elective termination of a pregnancy for medical reasons will be reported as an AE or SAE.
- Abnormal pregnancy outcomes (e.g., spontaneous abortion, fetal death, stillbirth, congenital anomalies, ectopic pregnancy) are considered SAEs and will be reported as such.

- The participant will be followed to determine the outcome of the pregnancy. The investigator will collect follow-up information on the participant and the neonate, and the information will be forwarded to the sponsor.
- Any post-study pregnancy-related SAE considered reasonably related to the study intervention by the investigator will be reported to the sponsor as described in Section.
- While the investigator is not obligated to actively seek this information in former study participants, he or she may learn of an SAE through spontaneous reporting.
- Any female participant who becomes pregnant while participating in the study will discontinue study intervention but may remain in the study (if consent is not withdrawn).

## 7. CONCOMITANT MEDICATION

### 7.1 Data Collection

Concomitant medications will be assessed from Enrollment to Discharge. The stop and start date, dose, brand name, generic name, and indication for each concomitant medication will be documented in source documents and on CRFs.

### 7.2 Disallowed Medications

Subjects will be prohibited from taking the following medications during the study:

- Inhaled short-acting muscarinic antagonist (SAMAs), such as ipratropium bromide.
- Inhaled therapies other than TRELEGY ELLIPTA containing any of the following: ICS, LAMA, or LABA.

## 8. PROTOCOL DEVIATIONS

Any event, whether planned or not, where the procedures as outlined in the documents approved by the IRB are not followed. Record all protocol deviations in the CRFs.

Report all unplanned deviations that involve a potential for increased risk to the subjects to the IRB within 10 days of occurrence or becoming aware of the occurrence. Report all unplanned deviations that do not involve increased risk to the subjects to the IRB at the next continuing review.

## **9. STATISTICAL ANALYSIS & DATA MANAGEMENT**

Continuous variables will be reported as means  $\pm$  standard deviations or medians [quartile 1, quartile 3], if skewed. Categorical variables will be reported as frequencies and percentages.

### **8.1. Measurement of Safety**

Safety will be assessed by monitoring vital signs, body weight, concomitant medication use, adverse events (AE), and serious adverse events (SAE).

### **8.2. Measurement of Efficacy**

Efficacy will be assessed by the number of in-hospital PRN respiratory therapy treatments with PRN nebulized albuterol 2.5mg, time in between PRN respiratory therapy, change in respiratory inspiratory flow rate measured by InCheck DIAL at medium resistance from baseline to discharge, length of stay, at-home drug compliance, 30-day re-admissions (all-cause and COPD exacerbation), 30-day survival, cost of in-hospital respiratory therapy, and response to a patient satisfaction questionnaire (QOL questionnaire).

Drug compliance at home will be assessed through follow-up phone call at 30-day post-discharge. Compliance will be calculated as the difference between 100 and the percentage of doses left on the TRELEGY ELLIPTA inhaler out of 30.

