#### **5.2.5 DISCHARGE**

Upon discharge, patients will receive a full TRELEGY ELLIPTA inhaler containing 30 doses with instructions to take 1 puff daily in the morning for 30 days. The in-hospital use TRELEGY ELLIPTA used by the patient will be discarded.

The following procedures/assessments will be done prior to hospital discharge:

- Spirometry (FEV1, FVC, FEV1/FVC)
- Peak inspiratory flow rate, measured by the InCheck Dial set at medium resistance.
- Concomitant Medications
- Adverse Events (AE) Assessment
- Patient Satisfaction Questionnaire (St George's Respiratory questionnaire, short version)

In addition, data from the specified assessments will be collected when available, and entered the case report forms (CRFS):

- Vital signs
- Withdrawal from protocol

If for any reason, some of the research assessments at discharge are not performed, the study team may (at investigator's discretion) schedule a follow-up with the subject in the research clinic to obtain the missed assessments.

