#### **d. Analysis of Secondary Endpoints**

Time (in days) in between PRN treatments, change in respiratory inspiratory flow rate from baseline to discharge, length of stay, at-home drug compliance, 30-day readmissions (all-cause and COPD/Asthma exacerbation), and 30-day survival will be compared between patients who were and were not readmitted using t-tests or chi-square tests (or Wilcoxon Rank Sum tests and Fisher's Exact tests), as appropriate.

The efficacy of the treatment protocol in the study cohort compared to the historical cohort will be assessed by comparing (1) the average number of PRN treatments per patient day while hospitalized estimated using a robust Poisson regression model (2) length of stay in the hospital, and (3) the rate of rehospitalization, using the Wilcoxon Rank sum test.

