#### **e. Reporting and Exclusions**

Missing data will not be imputed or carried forward in any of the analyses.

The sample size for continuous variables will be the number of subjects with non-missing data; in the summary of categorical variables, subjects with missing data will be excluded in the calculation of percentages.

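### At-home compliance is divided by a fixed 30 doses, so days back in hospital can be scored as missed doses and can create a false gap when readmitted and non-readmitted patients are compared

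*Combined protocol and SAP*

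**What the plan says.** Section 8.2 gives the timing and the formula. On timing: "Drug compliance at home will be assessed through follow-up phone call at 30-day post-discharge". On the score: "Compliance will be calculated as the difference between 100 and the percentage of doses left on the TRELEGY ELLIPTA inhaler out of 30". Section 5.2.5 explains the 30: "patients will receive a full TRELEGY ELLIPTA inhaler containing 30 doses with instructions to take 1 puff daily in the morning for 30 days".

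Section 8.7.d lists compliance among the secondary endpoints to be split by readmission status: "at-home drug compliance, 30-day readmissions (all-cause and COPD/Asthma exacerbation), and 30-day survival will be compared between patients who were and were not readmitted". For a continuous score such as this one, the section allows either a t-test or its rank-sum alternative. On gaps in the data, Section 8.7.e adds: "Missing data will not be imputed or carried forward in any of the analyses".

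The protocol does not say whether the take-home inhaler is used during a readmission. Sections 3.b and 3.c say that this product is rarely prescribed to inpatients with COPD and that short-acting therapy is the usual inpatient practice in this healthcare system. Section 5.2.5 also keeps the in-hospital inhaler, which is discarded at discharge, separate from the take-home one.

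**The concern.** Thirty is the right number of expected doses for a patient who is at home for all 30 days. It is too many for a patient who spends some of those days back in hospital without using the take-home inhaler. Those days leave doses on the counter, and the formula counts them as missed at home. Giving the same drug from hospital stock would not help, because the home counter would not move.

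Only readmitted patients have such days, so the grouping variable in 8.7.d enters the outcome through its denominator. The comparison is tilted towards lower compliance in readmitted patients whatever the patients do at home. The protocol plans publication (Sections 8.4 and 17), and evaluating the hospital-to-home transition is a secondary objective. A reader of the results could take such a gap as evidence that poor compliance led to readmission.

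**Working it through.** The plan gives no compliance figure, SD or power to reproduce. The check is therefore arithmetic on the formula, followed by its effect on the planned test.

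**Inputs from the protocol.** 30 doses for 30 days (5.2.5). 80 patients enrolled and 80% followed to day 30 (Section 4.a), so 80 × 0.80 = 64 patients. Rank-sum test or t-test (8.7.d).

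**Inputs assumed.** Readmission in 20% (0.20 × 64 ≈ 13 against 51), two-sided 5% level, readmission day uniform over days 1 to 30, stays of 2–4 or 3–7 days, home inhaler unused in hospital and use resumed afterwards. Daily at-home adherence is the same in both groups, with mean 80% and SD about 12 to 20 points.

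**Step 1: one patient.** Score = 100 − 100 × (doses left)/30. A patient who takes every dose due at home but spends L days in hospital scores 100 − 100 × L/30, a loss of 100/30 = 3.3 points per day:

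- L = 1: 96.7%
- L = 3: 90.0%
- L = 5: 83.3%
- L = 7: 76.7%
- L = 10: 66.7%

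**Step 2: the expected false gap.** A stay of s days that may run past day 30 loses on average s − s(s−1)/60 days within the window.

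- Averaged over s = 2 to 4: 3 − 0.11 = 2.89 days. Gap = 0.80 × 100 × 2.89/30 = 7.7, about 8 points.
- Averaged over s = 3 to 7: 5 − 0.37 = 4.63 days. Gap = 0.80 × 100 × 4.63/30 = 12.4, about 12 points.

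**Step 3: how often the test rejects, by simulation (13 against 51, equal at-home adherence).**

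| Stay | False gap | Rank-sum rejection, denominator 30 | Rank-sum rejection, days out of hospital |
|---|---|---|---|
| 2–4 days | about 8 points | about 39–48% | about 5% |
| 3–7 days | about 12 points | about 70–89% | about 5% |

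The range in each row comes from the SD. The smaller SD gives the higher rate.

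**Step 4: sensitivity.** A normal approximation with mean adherence 85%, SD 20 and 13 against 51 has standard error 20 × √(1/13 + 1/51) = 6.21. For 5 lost days the gap is 0.85 × 100 × 5/30 = 14.2, the ratio is 14.2/6.21 = 2.28, and rejection is Φ(2.28 − 1.96) ≈ 63%. The same sum gives 28% for 3 days and 89% for 7. Over 10 to 30% readmitted, 2 to 7 lost days and SD 10 to 25, the rate runs from 8% to nearly 100%.

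A second simulation (64 patients, 20% readmitted, 600 replicates per scenario) used a mean of 70% and SD of about 20. It gave rank-sum rejection of 15% at a mean of 3 lost days and 43% at 5. With mean 85% and SD about 16 the figures were 62% and 94%. In the same scenarios, dividing by days out of hospital left a mean difference of −0.4 to +0.4 points and rank-sum rejection of 2.7 to 6.0%.

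**The case against.** The strongest reply is that the bias depends on something the protocol does not state. If patients bring the take-home inhaler to hospital and use it there, 30 remains the right denominator and there is no artefact. This stands as a limit on the claim, and it is why the comparison *can* mislead rather than must. Nothing in the protocol provides for such use, however, and Sections 3.b and 3.c point the other way.

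It can also be said that this is one of several secondary comparisons, with no stated significance level and no causal claim, and that the rejection rates rest on assumed readmission rates, stays and SDs. That is fair. It limits the importance of the point, and it is why a range is given.

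Three stronger readings are tempting, and the documents do not support them.

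- A reader might infer that patients who die are scored as non-compliant. The reading comes from a phone call at day 30 and missing data are not imputed, so a deceased patient would ordinarily have no score. No proxy reading is described.
- A reader might infer that early or late calls bias the comparison. The call is set at day 30. No window is given, so individual scores could drift, but the comparison is biased only if timing differs by readmission status, and nothing suggests that it does.
- A reader might treat a patient who never resumes the inhaler after the readmission as part of the same artefact. Doses left unused once the patient is home again are missed at home. Dividing by days out of hospital does not remove that gap, nor should it.

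**Conclusion.** The concern holds in a limited form. A fixed denominator of 30, used in a comparison by readmission status, builds in a difference of 3.3 points for each inpatient day on which a fully adherent patient leaves the home inhaler unused. With typical stays assumed at 2 to 7 days, the false gap is about 8 to 12 points at 80% adherence. The false-positive rate is then well above 5% in most scenarios examined, though close to it in the mildest. The conclusion rests on the home inhaler being unused in hospital and resumed afterwards, and on assumed values for readmission rate, stay, SD and significance level.

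The score is sound for patients at home throughout, and the primary endpoint is not affected. The point is worth correcting because the direction of the bias is known in advance and the correction is cheap.

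**What to change.** In 8.2, define compliance as doses used (30 minus the counter reading) divided by days out of hospital from discharge to the reading. This equals 30 for a patient never readmitted and read at day 30. State whether the days of readmission and of discharge from it count as home days.

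Record the reading date, the readmission and readmission-discharge dates, and whether the home inhaler was used in hospital. Where it was, count those days in the denominator. Section 5.2.6 already provides for a call and a chart review but does not list these dates. The inhaler holds only 30 doses, so a late reading cannot be scored cleanly: five missed doses read at day 35 leave an empty counter. The reading date lets such cases be identified.

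In 8.7.d, use the redefined score and label the comparison descriptive, or drop it. A single day-30 reading cannot separate use before readmission from use after it, so even a correct score cannot show that low compliance came first. Restricting the analysis to doses before readmission would need a counter reading that the plan does not include.

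The cost is a few sentences in 8.2 and 8.7.d, a few extra fields on the follow-up form, and a denominator that differs between patients.

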### **8.3. Response Criteria**

N/A

### **8.4. Data Reporting**

It is intended that the results of the study will be published in at least one abstract for a scientific meeting and one manuscript.

## **8.5. Regulatory Requirements**

All subject records will only be identified by a unique screening number. Subjects' names are not to be transmitted to the Sponsor. The Investigator or designated site personnel will keep a master subject list containing the patient identification number, full name, date of birth, and hospital (or other) identification number of each subject.

## **8.6. Multicenter Guidelines**

This is a single-center study.

## **8.7. Statistical Considerations**

### **a. Study Design Endpoints**

Primary and secondary endpoints include the number of in-hospital PRN respiratory therapy treatments, time in between PRN respiratory therapy, change in peak inspiratory flow rate measured with an InCheck DIAL through medium low resistance from baseline to discharge, length of stay, at-home drug compliance, 30-day re-admissions (all-cause and respiratory), 30-day survival, cost of respiratory therapy, and QOL score.

### **b. Sample Size & Accrual Rate**

Enrollment of 80 patients.

### **c. Analysis of Primary Endpoint**

The number of PRN respiratory treatments during hospitalization will be reported as the median [quartile 1, quartile 3] and as the average number of PRN respiratory treatments per inpatient day  $\pm$  standard deviation. A comparison between patients who were and were not readmitted within 30-days will be made using a Wilcoxon signed rank test for the number of PRN respiratory treatments. Additionally, the incident rate ratio of the average per-inpatient

day PRN treatments will be estimated using a robust Poisson regression model comparing patients who were readmitted within 30-days to those who were not.

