## 2. OBJECTIVES & ENDPOINTS

### a. Primary Objective

1. To establish the requirements for PRN respiratory therapy treatments in patients hospitalized with the diagnosis of COPD exacerbation receiving once-daily ICS/LABA/LAMA (fluticasone furoate/umeclidinium/vilanterol) therapy.

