#### b. Therapy/Agent

TRELEGY ELLIPTA is supplied as a disposable light grey and beige plastic inhaler containing 2 foil strips, each with 30 blisters. One strip contains fluticasone furoate (100 mcg per blister), and the other strip contains a blend of umeclidinium and vilanterol (62.5 mcg and 25 mcg per blister, respectively). A blister from each strip is used to create one dose. The inhaler is packaged within a moisture-protective foil tray with a desiccant and a peelable lid.

It will be stored at room temperature between 68°F and 77°F (20°C and 25°C); excursions permitted from 59°F to 86°F (15°C to 30°C). It will be stored in a dry place away from direct heat or sunlight.

Subjects will be given TRELEGY ELLIPTA once daily at the same time every day ( $\pm$  2 hours). TRELEGY ELLIPTA will be initiated the morning of enrollment if feasible, or the morning following hospital enrollment otherwise. It will be administered as 1 inhalation by the orally inhaled route only.

*Although FDA approved, TRELEGY ELLIPTA is seldom prescribed to hospitalized COPD patients by treating physicians. Study participants will be consented prior to being prescribed TRELEGY ELLIPTA as part of this study.*

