#### **5.2.3 ENROLLMENT (within 24 hours of admission)**

The following procedures/assessments will be done the morning or following morning of admission into study:

- Concomitant Medications
- Adverse Events (AE) Assessment
- Patient Satisfaction Questionnaire (St George's Respiratory questionnaire-short version)

In addition, data from the specified assessments will be collected when available, and entered the case report forms (CRFs):

- Vital signs

- Physical Exam

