#### **5.2.4 TREATMENT (Enrollment to Discharge)**

TRELEGY ELLIPTA (fluticasone furoate 100 mcg, umeclidinium 62.5 mcg, and vilanterol 25 mcg inhalation powder) will be initiated on the morning of enrollment if feasible, or the morning after enrollment otherwise. Treatment will continue daily until discharge. Treatments will be administered by a respiratory therapist daily in the morning between 06:00 AM and 12:00 PM. Patients will receive nebulized short-acting beta-2 agonist (SABA) treatments of albuterol sulfate (2.5mg) as needed during hospitalization. Patients will receive prednisone 40 mg PO daily for the first 7 days from enrollment, subtracting 1 day for each consecutive day the patient received systemic corticosteroid treatment prior to enrollment.

Treatment procedures/assessments include:

- Concomitant Medications
- AE Assessment
- TRELEGY administration

Data from the following specified assessments will be collected daily, when available, and entered the case report forms (CRFs):

- Vital Signs
- Short-acting beta agonist (SABA) therapy: number and time of treatments

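### The primary PRN rate has no defined time window and, as worded, matches neither the period in which PRN use is collected nor the objective of PRN need while on study drug

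*Combined protocol and SAP*

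**What the plan says.** The primary objective (Section 2.a) concerns PRN need in patients "receiving once-daily ICS/LABA/LAMA (fluticasone furoate/umeclidinium/vilanterol) therapy".

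For the analysis, Section 8.7.c states: "The number of PRN respiratory treatments during hospitalization will be reported". It gives a median with quartiles and also "the average number of PRN respiratory treatments per inpatient day". The same per-day rate is the outcome of the Poisson model that compares readmitted with non-readmitted patients. Section 8.7.d compares a similar rate per hospitalized patient day with the historical cohort. Neither section says when day 1 starts, how part days count, or whether hours before enrolment or before the first dose are included.

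For data collection, Section 5.2.4, which covers enrolment to discharge, lists as a daily item: "Short-acting beta agonist (SABA) therapy: number and time of treatments". Section 7.1 uses the same period: "Concomitant medications will be assessed from Enrollment to Discharge". The chart review in Section 5.2.6 is for readmission.

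For timing, Sections 4.b.i and 5.2.3 allow enrolment up to 24 hours after admission. On the first dose, Section 3.b says: "TRELEGY ELLIPTA will be initiated the morning of enrollment if feasible, or the morning following hospital enrollment otherwise". Section 5.2.4 places dosing between 06:00 and 12:00.

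**The concern.** Three clocks are in play: admission, enrolment and first dose. The objective points to the third, data collection starts at the second, and the wording of the rate suggests the first. A rate whose numerator and denominator start at different times is diluted. A rate that starts both at admission mixes PRN use before the drug with PRN use on it.

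This is the primary estimate, and in a study without a concurrent control its value lies in the number itself. Any distortion also depends on length of stay, so it need not cancel when groups with different stays are compared, as in the readmission model or the historical comparison. The end of the window is open too: patients withdrawn under Section 4.b.ii or 6.4 may remain inpatients after they leave the study regimen.

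**Working it through.** The plan gives no expected PRN rate, length of stay or precision, so there is no figure of its own to reproduce.

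**Inputs from the protocol**
- Admission to enrolment: at most 24 h (Sections 4.b.i, 5.2.3).
- First dose: the morning of enrolment or the next morning (Sections 3.b, 5.2.4), between 06:00 and 12:00 (Section 5.2.4).
- Scheduled PRN collection: enrolment to discharge (Section 5.2.4).

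**Assumed inputs**
- Stay L = 3, 4, 5 or 7 days.
- k = pre-dose PRN rate divided by on-drug PRN rate, from 1 to 3.

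**Step 1. Longest time without study drug.** This is 24 h plus the time from enrolment to 12:00 the next day.
- Enrolled at 08:00: 24 + 28 = 52 h.
- Enrolled at 12:00: 24 + 24 = 48 h.
- Enrolled at 17:00: 24 + 19 = 43 h.

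About two days is therefore a realistic maximum for daytime enrolment. Only the part before enrolment, at most 24 h, lies outside scheduled PRN collection. The rest is undosed but recorded.

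**Step 2. Count from enrolment, days from admission, flat rate.** With g days uncollected, reported/true = (L − g)/L.

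| L (days) | g = 1 | Understatement | g = 0.5 | Understatement |
|---|---|---|---|---|
| 3 | 2/3 = 0.67 | 33% | 0.83 | 17% |
| 4 | 3/4 = 0.75 | 25% | 0.875 | 12.5% |
| 5 | 4/5 = 0.80 | 20% | 0.90 | 10% |
| 7 | 6/7 = 0.86 | 14% | 0.93 | 7% |

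**Step 3. Count and days both from admission.** With d undosed days, reported/on-drug = (k·d + L − d)/L.
- k = 1: 1.00 throughout.
- k = 2, d = 1: 1.33, 1.25, 1.20, 1.14 for L = 3, 4, 5, 7.
- k = 2, d = 2: 1.67, 1.50, 1.40, 1.29.

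**Step 4. Both effects together.** Take one uncollected day, then one collected but undosed day, with days counted from admission. Reported/on-drug = (k + L − 2)/L.
- k = 1: 0.67 to 0.86.
- k = 2: L/L = 1.00 for every stay.
- k = 3: (L + 1)/L = 1.33, 1.25, 1.20, 1.14.

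**Step 5. Count and days both from enrolment.** With one undosed day after enrolment, reported/on-drug = (k + L − 2)/(L − 1).
- k = 1: 1.00.
- k = 2: L/(L − 1) = 1.50, 1.33, 1.25, 1.17.

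With a dose at enrolment the ratio is 1.00.

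**Step 6. Carry-over into a group comparison.** Suppose two groups have equal true rates, stays of 3 and 7 days, and the Step 2 gap of one day. The apparent rate ratio is (2/3)/(6/7) = 0.78 instead of 1.00.

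**Step 7. Count and exposure both from first dose.** The ratio is 1.00 by construction.

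**The case against.** The strongest reply is that the protocol never says inpatient days run from admission. Section 5.2.4 schedules PRN collection from enrolment to discharge, and if the analyst uses that period for both count and days, the shortfall in Step 2 disappears. Same-morning dosing is the preferred course, so the remaining undosed time may be short. Section 8.7.d also speaks of the efficacy of the treatment protocol, for which a window from enrolment is a defensible target. All of this stands. It shows that a sound reading is available, but not that the plan chooses it: Section 8.7.c refers to the hospitalization and to inpatient days, whose ordinary meaning is the whole stay. Even the enrolment window departs from the objective when early PRN use is higher and the first dose is delayed (Step 5).

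A reader might also infer that up to two days of exposure carry no PRN count. They do not: the uncollected part is at most 24 h, and the two-day figure is a maximum for time without drug.

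A reader might further infer that the historical charts were counted from admission and that the comparison therefore favours the study cohort. Section 3.c says only that 60 charts were randomly selected after hospitalization. It gives no counting window, so this bias is possible but not shown.

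Pre-enrolment PRN use may be retrievable from hospital records, but the protocol does not plan to collect it. Section 8.7.e rules out imputation without saying whether uncollected hours are dropped from the exposure time.

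**Conclusion.** The concern holds as a misaligned and undefined window. The documents do not support the stronger statements that the rate is defined from admission or that the primary estimate is certain to be wrong in a known direction.

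Followed in its ordinary sense, the wording either places up to 24 h without scheduled PRN collection in the denominator or adds pre-drug PRN use to the numerator. Neither gives PRN need while receiving the drug. The first case understates the rate by 33%, 25%, 20% or 14% for stays of 3, 4, 5 or 7 days. Those figures rest on a full 24 h gap, a flat PRN rate and the assumed stays, and a 12 h gap halves them. The second case overstates the rate if early use is higher. In combination the effects can cancel exactly, as at k = 2 in Step 4. The documents give neither stay nor early PRN use, so size and sign are unknown before data. The window should be fixed before analysis.

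**What to change.** **Primary rate (Section 8.7.c).** Define it as PRN treatments from the first TRELEGY dose to discharge or withdrawal, divided by the hours in that interval/24. Use that exposure as the offset in the Poisson model. Report recorded PRN use between enrolment and first dose separately.

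**Data collection.** Record the clock time of the first dose on the CRF. Section 5.2.4 asks for SABA times but lists study drug administration without explicitly asking for its time.

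**Historical comparison (Section 8.7.d).** Use one identical window for numerator and denominator in both cohorts. One option is the whole stay, with the study cohort's pre-enrolment PRN use taken from the hospital chart. State that this window includes undosed time. An origin fixed at 24 hours after admission would not isolate on-drug time, because some patients may be first dosed later than that and others earlier.

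**Cost.** Analysis wording, one extra time to record, and some chart abstraction if the whole-stay window is used. The primary rate would rest on slightly less observed time per patient, shifted a little later in the stay. No change to patient care is needed.
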